4.7.2 Hypoglycemic events

During the trial, participants will be instructed to document any hypoglycemia events (including any possible reasons for hypoglycemia (eg, physical exercise, skipped meal)) in their eDiary. Hypoglycemia will be reported in the specific hypoglycemia event information form in the eCRF. The information recorded will include onset date and time; symptoms and/or signs; the SMPG value, if available; and the treatment, with documentation of whether the participant required outside assistance to achieve neurologic recovery. A hypoglycemia event that fulfills the seriousness criteria will also be documented on the SAE form in the eCRF.

Hypoglycemic events will be evaluated based on the following categories of interest (3, 4, 5):

- Any Hypoglycemic Event:
 - Any event recorded on the Hypoglycemic Event Information Library eCRF page that has “Yes” as the response to the question “Were any hypoglycemic events experienced”, regardless of the plasma glucose measurements.
- Confirmed hypoglycemia (symptomatic, severe) - each of the events below will be captured if the response to the question “Was a glucose measurement obtained at the time of the event before countermeasure?” on the Hypoglycemic Event Information Library eCRF page is “Yes”. Classification below will be dependent on glucose measurement.
 - ADA Level 1: A measurable glucose concentration of <70 mg/dL (3.9 mmol/L) but ≥ 54 mg/dL (3.0 mmol/L) that can alert a person to take action. A blood glucose concentration of 70 mg/dL (3.9 mmol/L) has been recognized as a marker of physiological hypoglycemia in humans. Recurrent episodes of hypoglycemia lead to increased hypoglycemia unawareness. Therefore, glucose levels <70 mg/dL (3.9 mmol/L) are clinically important, independent of the severity of acute symptoms.
 - ADA Level 2: A measurable glucose concentration of <54 mg/dL (3.0 mmol/L) that needs immediate action. At approximately 54 mg/dL (3.0 mmol/L), neurogenic and neuroglycopenic hypoglycemia symptoms begin to occur, ultimately leading to brain dysfunction at levels <50 mg/dL (2.8 mmol/L). Neuroglycopenic symptoms, including behavioral changes, visual changes, seizure, and loss of consciousness, are the result of central nervous system neuronal glucose deprivation.
 - ADA Level 3: A severe event characterized by altered mental and/or physical functioning that requires assistance from another person for recovery. Severe hypoglycemia captures events during which the symptoms associated with hypoglycemia affect a participant such that the participant requires assistance from others
- Documented Hypoglycemia (<70 mg/dL): event with a glucose level of <70 mg/dL (or <3.9 mmol/L) (with or without symptoms).
 - Documented Symptomatic Hypoglycemia: Any Documented Hypoglycemic event with a response of “Yes” to “Were symptoms present?” on the Hypoglycemic Event Information Library eCRF page will be considered a Documented Symptomatic Hypoglycemia event.

- Documented Serious Symptomatic Hypoglycemia: Any Documented Symptomatic Hypoglycemia where the participant also requires assistance from another person for recovery due to the participant's inability to help themselves (identified in the Hypoglycemic Event Information Library eCRF page as "Required Assistance Because Subject was not Capable of helping Self").
- Documented Non-Serious Symptomatic Hypoglycemia: Any Documented Symptomatic Hypoglycemia event as defined above where the participant does not require assistance from another person for recovery (identified in the Hypoglycemic Event Information Library eCRF page as "No Assistance" or "Received Assistance but Subject was Capable of Helping Self").
- Documented Asymptomatic Hypoglycemia: An event not accompanied by typical symptoms of hypoglycemia but with a measured plasma glucose concentration <70 mg/dL (3.9 mmol/L). Any event with a glucose level recorded as <70 mg/dL (3.9 mmol/L) on the Hypoglycemic Event Information Library eCRF that has "No" as a response to "Were symptoms present?" will be considered an Asymptomatic Hypoglycemia event.
- Probable Symptomatic Hypoglycemia: An event during which symptoms typical of hypoglycemia are not accompanied by a plasma glucose determination but was presumably caused by a plasma glucose concentration <70 mg/dL (3.9 mmol/L); symptoms treated with oral carbohydrate without a test of plasma glucose. An event will be considered a Probable Symptomatic Hypoglycemia event if the following conditions are met:
 - Response to the question "Was a glucose measurement obtained at the time of the event before countermeasure?" on the Hypoglycemic Event Information Library eCRF page is "No".
 - "Were symptoms present" is reported as "Yes" on the Hypoglycemic Event Information Library eCRF and at least one symptom is reported.
 - "Oral Carbohydrate" is marked "Yes" as a treatment of hypoglycemia on the Hypoglycemic Event Information Library eCRF page.
- Pseudo Hypoglycemia: An event during which the person with diabetes reports any of the typical symptoms of hypoglycemia with a measured plasma glucose concentration >70 mg/dL (>3.9 mmol/L) but approaching that level. Any event with a glucose level recorded as >70 mg/dL (>3.9 mmol/L) on the Hypoglycemic Event Information Library eCRF that has "Yes" as a response to "Were symptoms present?" and at least one symptom reported will be considered a Pseudo Hypoglycemia event.
- Nocturnal Hypoglycemia: Any hypoglycemia of the above categories defined by
 - Time of the day:
 - Between 00:00 AM and 05:59 AM regardless of whether the participant was awake or woke up because of the event.
 - "Time of Event" will be reported on the Hypoglycemic Event Information Library eCRF page. An event will be considered a Nocturnal Hypoglycemia Defined by

Time of the Day event depending on whether the reported time of the event falls into the range above.

- Sleep status:
 - A Nocturnal Hypoglycemic Event Defined by Sleep Status is an event in which the participant was asleep between bedtime and before getting up in the morning and was woken up because of the event (ie, the event occurred before the morning assessment of fasting prebreakfast SMPG and before any insulin injection).
 - Any event reported as “Between Bedtime and Waking” on the Hypoglycemic Information Library eCRF page as a response to the question “When did the Hypoglycemic Event occur?”, regardless of reported time of the event, will be considered Nocturnal Hypoglycemia Defined by Sleep Status).
- Daytime Hypoglycemia: Any hypoglycemia of the above categories defined by:
 - Time of the day:
 - Between 6:00 and 23:59 regardless of sleep status
 - “Time of Event” will be reported on the Hypoglycemic Event Information Library eCRF page. An event will be considered Daytime Hypoglycemia Defined by Time of the Day depending on whether the reported time of the event falls into the range above.
 - Awake status:
 - A Daytime Hypoglycemic Event Defined by Awake Status is any event that occurs while the participant was awake and before going to sleep.
 - Any event reported as “Between Waking and Bedtime” on the Hypoglycemic Information Library eCRF page as a response to the question “When did the Hypoglycemic Event occur?”, regardless of reported time of the event, will be considered Daytime Hypoglycemia Defined by Awake Status.

Hypoglycemia analyses will be presented separately for the following observation periods to evaluate the potentially increased risk of hypoglycemia during the initial 12 weeks after initiating basal insulin treatment:

- Overall 24-week treatment period
- Titration period (Week 1 through Week 12)
- Maintenance period (Week 12 through Week 24)

The following hypoglycemia events will be summarized. Analysis will include both the number and percentage of participants experiencing 1 event and the total number of events, summarized using descriptive statistics:

- Any hypoglycemia events, further summarized by:
 - Observation period
 - ADA classification level

- Diurnal distribution: 24 hour (all time), daytime, and nocturnal (0:00 to 5:59 inclusive)
- Documented Hypoglycemia, further summarized by:
 - Documented symptomatic hypoglycemia
 - Documented serious symptomatic hypoglycemia
 - Documented non-serious symptomatic hypoglycemia
 - Asymptomatic hypoglycemia
- Nocturnal Hypoglycemia Defined by Time of the Day, further summarized by:
 - ADA levels
- Nocturnal Hypoglycemia Defined by Sleep Status, further summarized by:
 - ADA levels
- Daytime Hypoglycemia Defined by Time of the Day, further summarized by:
 - ADA levels
- Daytime Hypoglycemia Defined by Awake Status, further summarized by:
 - ADA levels

Bar charts will also be produced for the percentage (%) of participants experiencing at least one documented hypoglycemia event, at least one daytime hypoglycemia event (defined by sleep status), and at least one nocturnal hypoglycemia event (defined by sleep status). Each bar chart will be produced overall, and by ADA level and observation period.

ORs and corresponding 95% CIs of the Gla-300 arm compared with the IDeg-100 arm will be calculated for the overall rate of on-treatment hypoglycemic events over the 24-week period using a logistic regression model that includes treatment arm and stratification factors at randomization as fixed factors based on OC. This analysis will be repeated for each observation period and by each level of diurnal distribution and ADA level. In addition to the summary table, a forest plot will be produced for this analysis.

The overall rate of hypoglycemic events in participant-months of exposure will also be calculated and presented by treatment arm for the entire 24-week period, and then repeated for each observation period, diurnal distribution, and ADA level. The rate ratios and corresponding 95% CIs of the Gla-300 arm over the IDeg-100 arm for hypoglycemic events in patients-months of exposure will be estimated using a negative-binomial regression adjusted for stratification factors at randomization with time on treatment as an offset. In addition to the summary table, a forest plot will be produced for this analysis.

The formula for the sample hypoglycemic events rate in patients-months of exposure is:

$$\text{Hypoglycemic event rates per patient-month of exposure} = \frac{\text{Number of participants with hypoglycemic events}}{\text{Total participant-months of exposure}}$$

Total participant-months of exposure is calculated as shown below:

$$\text{Total participant-months of exposure} = \frac{12 \times (\sum_{i=1}^n x_i)}{365.25}$$

$$x_i = (\text{last dose date for } i^{\text{th}} \text{ participant} - \text{first dose date for } i^{\text{th}} \text{ participant} + 1)$$

The number as well as the rate of nocturnal hypoglycemic events (as defined by sleep status) in patient-months of exposure will also be summarized.

In addition, the distribution of the total occurrence of each episode of documented hypoglycemia will be presented by 2-hour timeframe over 24 hours during the 24-week treatment. This will be repeated for each category of documented hypoglycemia.

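### ADA Level 3 is made conditional on a glucose reading before treatment, so assisted events without one drop out of the severe count

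*SAP*

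**What the plan says.** SAP section 4.7.2 lists the three ADA levels beneath a single heading for confirmed hypoglycemia. The rule at that heading is that "each of the events below will be captured if the response to the question" on a prior reading is Yes. The eCRF item it refers to is worded: "Was a glucose measurement obtained at the time of the event before countermeasure". The next sentence reads: "Classification below will be dependent on glucose measurement". No exception is made for Level 3.

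The Level 3 entry beneath that rule contains no glucose value. It rests on altered functioning and need for help: "Severe hypoglycemia captures events during which the symptoms associated with hypoglycemia affect a participant such that the participant requires assistance from others". Protocol section 6.2.2 defines Level 3 in the same way and notes that needing assistance means the person could not help themselves.

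Three other SAP categories in the same section bear on the point:

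- Any Hypoglycemic Event is counted "regardless of the plasma glucose measurements".
- Documented Hypoglycemia, the parent of Documented Serious Symptomatic Hypoglycemia, is an "event with a glucose level of <70 mg/dL". The serious subcategory also needs the eCRF response "Required Assistance Because Subject was not Capable of helping Self".
- Probable Symptomatic Hypoglycemia needs no reading, but it needs symptoms and oral carbohydrate marked Yes "as a treatment of hypoglycemia on the Hypoglycemic Event Information Library eCRF page". It does not use the assistance response.

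**The concern.** The capture rule and the definition it governs do not fit together. A rule that classifies by glucose value has nothing to act on for Level 3, which has no glucose cut-off. A rule that first requires a reading before treatment removes events that the definition would include.

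The protocol foresees such events. Section 6.1.5 asks for a reading before carbohydrate or glucose is given, unless safety calls for immediate rescue, and the event form records the glucose value only where one is available. A participant who cannot help themselves is a natural case for treating first, so missing readings may concentrate among the worst events. That last step is inference; neither document gives a rate.

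Severe hypoglycemia is a named category of the safety endpoint in SAP section 1.2. After early termination the abbreviated CSR focuses in part on safety (SAP Appendix 2), and Table 14.3.7, which reports hypoglycemia by ADA level, is kept (SAP Appendix 6). At stake is whether the severe count in that table follows its own definition.

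**Working it through.** No planned figure is involved, so the check is to take one test event through the rules and then write down the count in general terms.

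**Test event.** Symptoms present; the participant could not help themselves and was assisted; the eCRF answer on a reading before countermeasure is No.

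| Category (SAP section 4.7.2) | Requirement | Test event |
|---|---|---|
| Any Hypoglycemic Event | Recorded on the event page, with or without glucose | Counted |
| ADA Level 1 | Reading before countermeasure; 54 to below 70 mg/dL | Not counted |
| ADA Level 2 | Reading before countermeasure; below 54 mg/dL | Not counted |
| ADA Level 3 | Assistance needed, but under the same reading condition | Not counted |
| Documented Serious Symptomatic | Glucose below 70 mg/dL, symptoms, assistance | Not counted |
| Probable Symptomatic | No reading, symptoms, oral carbohydrate marked Yes | Only if oral carbohydrate was given; assistance not shown |

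Protocol section 5.8.1 names glucagon or intravenous glucose as possible treatment for episodes with coma, seizure or neurologic impairment. An event treated only in that way also fails Probable Symptomatic. It is then in the overall count with no ADA level. Under the protocol 6.2.2 definition, the same event is Level 3.

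**Is there another route to Level 3?** The SAP later breaks all hypoglycemia events down by ADA level, but section 4.7.2 is the only place that defines the levels, and it does so under the glucose rule. Appendix 2 does not list the condition among changes to protocol-planned analyses.

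**Count.** Let N be the number of events with the assistance response, and k the number of those with No for a reading before countermeasure.

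- As written: Level 3 count ≤ N − k. It is an upper bound because classification also depends on the value obtained, and Level 3 has no cut-off.
- With Level 3 taken from the assistance response: Level 3 count = N.
- Undercount ≥ N − (N − k) = k, that is, at least 1 per affected event.

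Neither N nor k is in the documents. Writing q = k/N, the share captured is at most 1 − q. Over an assumed range this gives:

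- q = 0.10: 1 − 0.10 = 90%
- q = 0.30: 1 − 0.30 = 70%
- q = 0.50: 1 − 0.50 = 50%

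These values of q illustrate the arithmetic and are not estimates for this trial.

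**The case against.** **The wording is if, not only if.** The Level 3 entry has its own sentence about what it captures, and the ADA breakdown is applied to all hypoglycemia events, which are defined without regard to glucose. A programmer might therefore count the event as Level 3. This does not rescue the text. The sentence after the condition makes classification depend on the measurement, and the later breakdown only uses levels already defined under that rule. A programmer who reached the right count would be setting the written rule aside.

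**The grouping comes from the protocol.** This is true: section 6.2.2 also places Level 3 under confirmed hypoglycemia, and section 6.1.5 speaks of confirmation by meter value. But the protocol sets no condition that a reading precede countermeasure. The only cut-offs it attaches to confirmed events are 70 and 54 mg/dL, which are the Level 1 and Level 2 thresholds.

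**The consequence is small.** Much of this stands. The first participant was randomized on 20 December 2022, and the sponsor stopped the trial on 27 June 2023 for slow recruitment. The odds ratios, rate ratios and bar charts by ADA level are not in the abbreviated list. Safety analysis is descriptive, without formal testing. Affected events stay in the overall count, in Listing 16.2.7.4 if on treatment, and in SAE reporting if serious. Nothing shows that any such event occurred.

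**The SAE table is not a check on Level 3.** This stands too. Needing assistance and being serious are different criteria, so Tables 14.3.5 and 14.3.7 can differ even when both are correct. An event with seizure and no prior reading could appear in the first and be missing from Level 3 in the second. That is a visible consequence of the rule, not the evidence for it.

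**Levels can overlap.** An assisted event below 54 mg/dL meets both Level 2 and Level 3. That overlap is in the SAP already, with or without the change proposed here.

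**Conclusion.** The concern holds. As written, SAP section 4.7.2 leaves an assisted event with no reading before countermeasure out of ADA Level 3, contrary to the definition of Level 3 in both documents, and no other category shows it as severe. The Level 3 count in Table 14.3.7 is too low by at least one for each such event. The number of affected events and any difference between arms are unknown.

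The conclusion assumes that the table is programmed as the SAP is worded; its shell is not in the documents. The effect is confined to one severity count in a descriptive safety output and does not touch the primary analysis. It should be fixed because the count concerns a named safety category in a table that will be reported.

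**What to change.** In SAP section 4.7.2:

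1. Limit the condition on a reading before countermeasure, and the classification by glucose value, to ADA Levels 1 and 2.
2. Derive ADA Level 3 from the existing eCRF response "Required Assistance Because Subject was not Capable of helping Self", whatever the availability or value of glucose.

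The Documented Hypoglycemia categories can stay as they are. Two optional additions would help: a footnote to Table 14.3.7 giving the number of Level 3 events without a glucose value, and a sentence saying how an event that meets both Level 2 and Level 3 is tabulated.

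The cost is a short wording change and a small programming change to Table 14.3.7. No new data are needed, since the assistance item is already collected. The downside is that some Level 3 events will lack biochemical confirmation, which the footnote would make visible. If the table has already been produced, comparing the eCRF assistance responses with its Level 3 count will show whether a correction is needed.

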8.7.6.2 Hypoglycemia

The number and incidence of patients experiencing at least 1 hypoglycemic event will be presented by treatment arm and type of hypoglycemic event (ADA category) according to the diurnal distribution.

The ORs and corresponding 95% CIs of the Gla-300 arm compared with the IDeg-100 arm will be estimated for each hypoglycemic event using a logistic regression model that includes treatment arm and stratification factors at randomization as fixed factors based on observed cases.

The number and rate of hypoglycemic events (in patient-month of exposure) will be determined by treatment arm and type of hypoglycemic event (ADA category), according to the diurnal distribution. For each hypoglycemic event, the rate ratios and corresponding 95% CIs of the Gla-300 arm over the IDeg-100 arm will be estimated using a negative-binomial regression adjusted for stratification factors at randomization with time on treatment as an offset.

The number and incidence of patients experiencing at least 1 nocturnal hypoglycemic event defined by sleep status and the number and rate of these nocturnal events (in patient-month of exposure) will also be presented by treatment arm.

The aforementioned hypoglycemia analyses will be performed and presented separately for the overall 24-week study treatment period, the titration period (ie, Week 1 through Week 12), and the maintenance period (ie, Week 13 through Week 24).

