- The **pre-treatment period** (up to 2 weeks) is defined as the time between the date of signed informed consent and the first injection of the open-label study drug.
- The **on-treatment period** (24-weeks) is defined as the 24-week open-label treatment period. The on-treatment period includes a 12-week titration period where study drug doses will be adjusted using a recommended dose-adjustment algorithm, as well as a 12-week maintenance period at the titrated dose.
- The **post-treatment period** is defined as the 7-day, post-treatment, safety follow-up period after the last dose of the study drug or after premature/permanent discontinuation from study drug treatment.

The on-study period is defined as the time from the date of signed informed consent until the end of the study defined as the last scheduled visit for those who completed the study and the end-of-study date (“Status Date”) collected on electronic case report form (eCRF) page “Completion of End of Study” for those who did not complete the study. If death is the end-of-study reason, date of death will be used.

The observation period used for safety analyses is described in [Section 4.7](#).

The maximum trial duration per participant will be 27 weeks.

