4.7 SAFETY ANALYSES

All safety analyses will be performed on the safety population as defined in [Section 3](#), unless otherwise specified, using the common rules:

- The analysis of the safety variables will be essentially descriptive, and no formal hypothesis testing is planned.
- Safety data in participants who do not belong to the safety population (eg, exposed but not randomized) will be provided separately.

The observation period of safety data will be divided into 3 periods as defined below:

- **Pre-treatment period:** the time between the date of signed informed consent and the first injection of the open-label study drug.
- **On-treatment period:** the time from the first injection of the open-label study drug up to 7 days after the last injection of the open-label study drug, regardless of the introduction of rescue therapy. The 7-day interval is chosen based on the half-life of the study drug (approximately 5 times the half-life of IDeg-100).
- **Post-treatment period:** the time starting 8 days after the last injection of the open-label study drug.

The denominator for computation of percentages is the safety set within each treatment arm unless otherwise specified.

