4.7.1 Extent of exposure

The extent of IMP exposure will be assessed by the duration of IMP exposure, compliance, and dose and summarized within the safety population.

Duration of IMP exposure

Duration of IMP exposure (in days) is defined as last IMP administration date - first IMP administration date +1 day, regardless of unplanned intermittent discontinuations. If the date of the last dose of IMP is missing, the duration of IMP will be left as missing.

Duration of IMP exposure (in weeks) is defined as (Last day of exposure - first day of exposure +1)/7. Duration of IMP exposure (in weeks) will be summarized quantitatively using descriptive statistics and categorically as below:

- ≤ 12 weeks
- > 12 weeks to ≤ 24 weeks
- > 24 weeks

Additionally, cumulative duration of treatment exposure expressed in participant-years will be calculated, defined as the sum of days of the duration of treatment exposure for all participants divided by 365.25.

Treatment compliance

A given administration will be considered noncompliant if the participant did not receive a once daily administration between 6:00 AM and 8:00 PM as required by the protocol. No imputation will be made for participants with missing or incomplete data.

Percentage of treatment compliance for a participant will be defined as the number of injections that the participant was compliant divided by the total number of injections that the participant was planned to take from the first administration of IMP up to the actual last administration of IMP multiplied by 100.

The number of planned injections is equal to the duration of IMP exposure (in days).

Treatment compliance will be summarized quantitatively using descriptive statistics and will also be summarized categorically: <60%, ≥60% to <80%, ≥80% to ≤100%, >100%.

Cases of overdose will constitute AESIs and will be listed as such.

Dosing

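### Week 12 is counted in both the titration and the maintenance period, and the only exposure formula for hypoglycaemia rates is not cut by period

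*SAP*

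**What the plan says.** **Periods.** SAP 4.7.2 presents hypoglycaemia for the overall 24 weeks and for two sub-periods: "Titration period (Week 1 through Week 12" and "Maintenance period (Week 12 through Week 24". Protocol 8.7.6.2 has "the maintenance period (ie, Week 13 through Week 24". Protocol 6.2.2 splits the trial into up to 12 weeks, and more than 12 up to 24 weeks. SAP 4.1, defining the observation period for non-safety analyses, describes 12 weeks of titration "as well as a 12-week maintenance period at the titrated dose". SAP Appendix 2, which lists changes from the protocol, does not mention the period boundary.

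**Exposure.** SAP 4.7.2 gives one formula, introduced by "Total participant-months of exposure is calculated as shown below": last dose date minus first dose date plus 1, summed over participants and converted to months. The same section repeats the rates by observation period and uses time on treatment as the offset of the negative-binomial model. Protocol 6.2.2 divides by the days of exposure that fall inside the time window.

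**Events.** SAP 4.7 defines the on-treatment period for safety data as running "up to 7 days after the last injection of the open-label study drug". SAP 4.7.2 applies the odds-ratio model to the "overall rate of on-treatment hypoglycemic events over the 24-week period". The rate paragraph that follows speaks of the 24-week period and does not repeat the term on-treatment.

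**The concern.** SAP 4.7.2 says the split is there to see whether risk is raised in the first 12 weeks after basal insulin is started. A week that sits in both periods blurs that contrast at its boundary.

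A rate by period also needs a denominator for that period. With a single whole-treatment denominator, the period figures are not rates over the period they are labelled with. A participant who stops in titration also adds exposure to a maintenance period that he or she never entered.

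Hypoglycaemia by period is a named safety endpoint in both documents, so the definitions should leave no choice to the programmer.

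**Working it through.** The documents state no hypoglycaemia count or rate, so there is no figure of the plan to reproduce. The checks below compare window lengths. They assume a constant event rate and, for a completer, 24 × 7 = 168 days of dosing.

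**1. Overlap (SAP 4.7.2 against Protocol 8.7.6.2).**
- Weeks 13–24: 12 weeks = 84 days. Weeks 12–24 inclusive: 13 weeks = 91 days.
- Full week shared: 91/84 = 1.083, so maintenance event counts rise by 8.3%. The two periods together cover 84 + 91 = 175 days, and 175/168 = 104.2% of the overall count.
- Only the visit day shared (Week 12 read as the Week 12 visit): 85/84 = 1.012, or +1.2%. The sum is 169/168 = 100.6%.
- This concerns event counts. Numbers of participants with an event need not add up across periods under any definition.

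**2. Whole-treatment exposure used for a period rate (SAP 4.7.2 against Protocol 6.2.2).**
- Completer, either period: 84 days at risk, but divided by 168. 84/168 = 0.50, so the rate is halved.
- Participant whose last dose is on Day 28: 0 days at risk in maintenance, but 28 days enter its denominator.
- The two periods are not affected equally once some participants stop early. Assume 15% stop at Day 28. Mean exposure is 0.85 × 84 + 0.15 × 28 = 75.6 days in titration, 0.85 × 84 = 71.4 days in maintenance, and 147.0 days in total. The literal rates are 75.6/147 = 0.514 and 71.4/147 = 0.486 of the true rate. Titration then looks 75.6/71.4 = 1.06 times as risky as maintenance when the true rates are equal.

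**3. Seven-day tail, if on-treatment events feed the rates.** Excess = 7 / exposure days:

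| Exposure (days) | Excess |
|---|---|
| 168 | 4.2% |
| 84 | 8.3% |
| 28 | 25.0% |

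Effect on the rate ratio under assumed stopping at Day 28:
- 5% against 15%: mean exposures are 161 and 147 days; (168/161)/(154/147) = 1.0435/1.0476 = 0.996, a shift of 0.4%.
- 0% against 30%: mean exposures are 168 and 126 days; (175/168)/(133/126) = 1.0417/1.0556 = 0.987, a shift of 1.3%.

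The documents give no discontinuation pattern, so these shares are assumptions.

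**The case against.** **The overlap may be a slip of wording.** The protocol and SAP 4.1 both imply separate periods. In the schedule of events Week 12 is a visit on Day 84, so the SAP may mean visit to visit, which leaves one shared day. That is fair, and it is why both sizes are given. Even so, the text as written puts Week 12 in both periods. Nor does the overlap by itself bias a rate: if events and exposure both include Week 12, each period's rate is sound. The harm is to the counts and to the contrast at the boundary.

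**The 7-day tail is not a stated rule for the rates.** A reader might infer that it is, because SAP 4.7.2 analyses on-treatment events. That phrase stands in the logistic-regression paragraph, which uses no exposure. The inference still has support: SAP 4.7 defines on-treatment for all safety data, Protocol 8.7.6.1 labels the window including the 7 days as 24-week, and hypoglycaemia is recorded at the Week 25 contact. It is probable, not certain. The sizes in step 3 also assume that the event rate does not fall after the last dose.

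**Missing last-dose dates.** SAP 4.7.1 says: "If the date of the last dose of IMP is missing, the duration of IMP will be left as missing". A reader might infer that such a participant loses exposure but keeps events in the rate. The documents do not say so. In the negative-binomial model a record with a missing offset is normally dropped, so events and exposure leave together. Only the crude rate could be affected, and the SAP is silent on which participants enter its numerator.

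**Early termination reduces the weight.** SAP Appendix 6 keeps a hypoglycaemia overview by period (Table 14.3.7) and a listing of on-treatment events (Listing 16.2.7.4). It names no rate or rate-ratio table, and SAP 4.7 makes the safety analysis descriptive. This stands for the rate part. It does not remove the overlap, which affects Table 14.3.7.

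**Conclusion.** The period definition in SAP 4.7.2 is wrong as written: it conflicts with two sections of the protocol and with SAP 4.1, and it affects a table that is still planned. The size is 8.3% of maintenance event counts for a shared week or 1.2% for a shared day, at a constant event rate.

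The exposure formula is incomplete for rates by period. Taken literally it halves a completer's period rate and departs from Protocol 6.2.2. A programmer would probably notice, but the SAP gives no other rule.

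The 7-day mismatch depends on an unstated choice. It is 4.2% for a completer and up to 25% at 28 days of exposure, and it shifts the rate ratio by about 0.4% to 1.3% under the assumed imbalances.

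The documents do not support a claim that missing last-dose dates bias the modelled rates, or that the comparison between arms is materially distorted. This is a correction that should be made; it does not threaten the trial's main conclusions.

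**What to change.** - Define titration as Days 1–84 and maintenance as Days 85–168, with Day 1 the day of first dose, as in the SAP's analysis-window table. Assign each event by its onset date.
- Choose one end point for events and exposure alike: last dose for both, or last dose + 7 days for both. Either choice matches the windows.
- Compute time at risk in each period as max(0, min(chosen end point, end of study, period end) − period start + 1). The floor is needed: with last dose on Day 28 and a 7-day tail, maintenance would otherwise give 35 − 85 + 1 = −49 days. A participant with zero time does not contribute to that period.
- Use this variable in both the crude rates and the model offset, and count only events that fall in the same interval.
- State that the crude rate uses the same participants in numerator and denominator, including when a last-dose date is missing.

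The cost is SAP wording and one derived variable. Period rates would rise relative to the literal formula, to about double for completers. Rates whose events include the 7-day tail would fall slightly if the tail is added to exposure. For the abbreviated report only the period boundary needs changing, unless a rate table is added.
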